12.4 Analysis of Secondary Endpoints

All secondary endpoints will be summarized by descriptive statistics. Group comparisons will be carried out using appropriate statistical tests in an exploratory fashion.

12.5 Analysis of Exploratory Endpoints

Exploratory endpoints will be descriptive.

12.6 Analysis of Safety Data

Safety data will be descriptive as we expect a low number of non-hematologic adverse effects. Hematologic adverse effects and associated infections are common with this regimen in standard practice, including hospitalizations. We do not expect any additional adverse effects with the change in this schedule.

12.7 Interim Analysis and Stopping Rules

No interim analysis for efficacy will be planned. However, the study will be monitored and stopped following statistical rules. Sequential boundaries will be used to monitor neurological dose-limiting toxicities (DLT) (Grade 3-5) rate. The accrual will be halted if

excessive numbers of DLTs are seen, that is, if the number of DLT is equal to or exceeds the Boundary (b_n) out of the accrued subjects (n) with full follow-up (see table 12.7.1). This is a Pocock-type stopping boundary that yields the probability of crossing the boundary at most 5% when the rate of DLT is equal to the acceptable rate 10%. This boundary is equivalent to testing the null hypothesis, after each subject, that the event rate is equal to 10%, using a one-sided level 0.01 test.

Table 12.7.1

The trial will be stopped if the number of neurological DLT (grade 3-5) is equal to or exceeds the **Boundary (b_n)** out of the total **Number of Subjects (n)** participating in the trial with completed follow-up.

Number of subjects (n)									
1	2	3-6	7-10	11-16	17-21	22-28	29	30	
Boundary (b_n)									
-	2	3	4	5	6	7	8	-	

12.8 Data Integrity and Safety Committee

This protocol will be reviewed and monitored by the University of Florida Health Cancer Center Data Integrity and Safety Committee (UFHCC DISC) in accordance with their policies and procedures. They will review and monitor study progress, toxicity, safety and other data from this trial. Questions about subject safety or protocol performance will be addressed with the sponsor-investigator, statistician and study team members. Should any major concerns arise, the DISC will offer recommendations regarding whether or not to suspend the trial.

UFHCC DISC data and safety monitoring activities include:

- Review of clinical trial conducted for progress and safety
- Review of all adverse events requiring expedited reporting as defined in the protocol
- Review of reports generated by data quality control review process
- Notification of the sponsor-investigator of recommended action
- Notification of sites coordinated by the UFHCC of adverse events requiring expedited reporting and subsequent committee recommendations for study modifications

In compliance with the UFHCC data and safety monitoring plan, the PI will provide a Data Integrity and Safety Committee Report to DISC at the predetermined timelines for the level of risk category assigned during the initial SRMC (Scientific Review and Monitoring Committee) review, which occurs prior to initial IRB approval.

UFHCC investigator-initiated protocols will be classified into one of the following categories

of risk by the SRMC (see SRMC manual for further details):

Level 1 – Low risk Investigator Initiated interventional trials.

Level 2 – Moderate risk Investigator Initiated or externally sponsored interventional (such as drug, biologic or device) trials using FDA approved or commercially available compounds or interventions.

Level 3 – High risk Investigator Initiated or externally sponsored interventional trials (such as investigator-sponsored INDs, Phase I trials, studies requiring biosafety approval, or other areas that may be designated by NIH as high risk).

Level 4 – Complex trials involving very high risk to subjects and a high level of complexity such as first in human or gene transfer studies.

The risk level assigned by SRMC will determine the appropriate level of DISC monitoring required, with increased monitoring required for higher-risk trials.

Findings will be communicated to all study sites by UFHCC CRO.

12.9 Data Monitoring

UFHCC (University of Florida Health Cancer Center) Quality Assurance team and/or project management officers will perform remote monitoring and may make monitoring visits to the trial sites periodically during the trial to confirm that all sites are complying with the protocol. Source documents will be reviewed for completion and validated against data submitted electronically via Electronic Data Capture. The site investigator/institution guarantee access to source documents by UFHCC or its designee and appropriate regulatory agencies. As part of the responsibilities assumed by conducting this study, the Principal Investigator (PI) agrees to maintain and have available for monitoring adequate case records (accurate source documents and CRFs) for the subjects treated under this protocol.

The trial site may also be subject to quality assurance audit by any collaborating sponsors or their designee as well as inspection by appropriate regulatory agencies.

It is important for the site investigator and their relevant personnel to be available during the monitoring visits and possible audits and for sufficient time to be devoted to the process.

12.10 Principal Investigator Responsibilities

Per UF IRB requirements, the PI is personally responsible for conducting and supervising the conduct of human research subjects by “protecting the rights, safety, and welfare of subjects under the investigator’s care.” The PI also must ensure that all the research conducted is done so in an ethical manner and in accordance with all federal, state, and local laws and regulations, institutional policies, and the requirements of the IRB.

Oversight is defined as “management by overseeing the performance or operation of a person or group; watchful care, superintendence, general supervision”. Any person serving as a PI has voluntarily accepted these responsibilities and is expected to fully comply with these requirements, as outlined in the UFHCC Guidance: *Principal Investigator Responsibilities and Oversight*.

The PI will be primarily responsible for continuous monitoring of adverse events, protocol violations, and other immediate protocol issues. The study coordinator will collect information on subjects enrolled through the use of electronic or paper adverse event (AE) forms, CRFs, and Informed Consent forms.

13. EMERGENCY PROCEDURES

13.1 Emergency Contact

In emergency situations, the treating physician should contact the Principal Investigator by telephone at the number listed on the title page of the protocol.

13.2 Emergency Treatment

During and following a subject’s participation in the study, the treating physician and/or institution should ensure that adequate medical care is provided to a subject for any adverse events, including clinically significant laboratory values, related to the study.

14. ADMINISTRATIVE, ETHICAL, AND REGULATORY CONSIDERATIONS

14.1 Good Clinical Practice

The procedures set out in this study protocol pertaining to the conduct, evaluation, and documentation of this study are designed to ensure that the Principal Investigator and Co-Investigators abide by Good Clinical Practice (GCP), as described in International Conference on Harmonization (ICH) Guideline E6 and in accordance with the general ethical principles outlined in the Declaration of Helsinki.

The study will be conducted in compliance with the protocol. The protocol, any amendments, and the subject informed consent will receive Institutional Review Board (IRB) approval before initiation of the study.

The Principal Investigator will conduct all aspects of this study in accordance with applicable national, state, and local laws of the pertinent regulatory authorities.

All potential serious breaches must be reported immediately to the UFHCC Project Management Office (PMO, [contact], who will then report the breach to UFHCC DISC) and the IRB of record, if applicable. A serious breach is a breach of the conditions and principles of GCP in connection with the study or the protocol, which is likely to affect, to a significant degree, the safety or physical or mental integrity of the subjects of the study or the scientific value of the study.

14.2 Institutional Review Board

Before study initiation, the investigator must have written and dated approval from the IRB for the protocol, consent form, subject recruitment materials/process (e.g., advertisements), and any other written information to be provided to subjects. The investigator should also provide the IRB with a copy of the Investigator Brochure or product labeling, information to be provided to subjects, and any updates. The investigator should provide the IRB with reports, updates, and other information (e.g., amendments, and administrative letters) according to regulatory requirements or institution procedures.

14.3 Compliance with Laws and Regulations

It is intended that the proposed study be conducted according to the International Conference on Harmonization E6 Guideline for Good Clinical Practice (GCP) and the Declaration of Helsinki.

Please refer to the International Conference on Harmonization and GCP:

<http://www.fda.gov/oc/gcp/guidance.html>; Declaration of Helsinki:

<http://www.fda.gov/oc/health/helsinki89.html>; Code of Federal Regulations, Title

21: <http://www.accessdata.fda.gov/scripts/cdrh/cfdocs/cfcfr/CFRSearch.cfm>

All UF Health Cancer Center investigator-initiated trials, meeting the criteria of the FDAAA's applicable clinical trials, will be registered with [ClinicalTrials.gov](https://clinicaltrials.gov) by the Project Management Officer (PMO) or assigned designee. All studies must be registered prior to enrollment of the first participant. The Project Management Officer or assigned designee will maintain the responsibility of updating trials registered with ClinicalTrials.gov. Per FDA requirement, information must be updated at least every twelve months and the registry must be updated within thirty days of any changes in recruitment status or completion of the study. The PMO will determine if registration and updates to the NCI CTRP are required.

14.4 Delegation of Investigator Responsibilities

The Principal Investigator will ensure that all persons assisting with the study are adequately informed about the protocol, any amendments to the protocol, the study treatments, and their study-related duties and functions. The Principal Investigator will maintain a list of Co-Investigators and other appropriately qualified persons to whom he has delegated significant study-related duties.

Study personnel involved in conducting this study will be qualified by education, training, and experience to perform their respective tasks. This study will not use the services of study personnel where sanctions have been invoked or where there has been scientific misconduct or fraud (e.g., loss of medical licensure; debarment). Systems with procedures that ensure the quality of every aspect of the study will be implemented.

14.5 Subject Information and Informed Consent

Before being enrolled in this clinical trial, the subject must consent to participate after the nature, scope, and possible consequences of the clinical study have been explained in a form understandable to him or her. An informed consent document that includes both information about the study and the consent form will be prepared and given to the subject. This document will contain all ICH, GCP, and locally required regulatory elements. The document must be in a language understandable to the subject and must specify the person who obtained informed consent.

After reading the informed consent document, the subject must give consent in writing. The written informed consent will be obtained prior to conducting any study-related procedures or tests. The subject's consent must be confirmed at the time of consent by the personally dated signature of the person conducting the informed consent discussions and a copy of the consent form (preferably signed) must be given to the subject for their records.

The PI will retain the original signed consent document. The PI will not undertake any measures specifically required only for the clinical study until valid consent has been obtained.

14.6 Confidentiality

All records identifying the subject will be kept confidential and, to the extent permitted by the applicable laws and/or regulations, will not be made publicly available.

Should direct access to medical records require a waiver or authorization separate from the subject's statement of informed consent, it is the responsibility of the Investigator to obtain such permission in writing from the appropriate individual.

Subjects will be told that the IRB, UF Health DISC, or regulatory authorities may inspect their medical records to verify the information collected, and that all personal information made available for inspection will be handled in strictest confidence and in accordance with local data protection law.

14.7 Protocol Amendments

Once the study has started, amendments should be made only in exceptional cases. Protocol amendments will not be implemented without prior written IRB approval. All amendments

will be submitted to the IRB and SRMC (as applicable), and written verification that the amendment was submitted and subsequently approved is to be obtained, and notification will sent out to the applicable study teams, prior to implementing the amendment.

On an emergency-basis, to eliminate an immediate safety hazard to a subject, a protocol deviation may be implemented immediately, provided the IRB and UFHCC CRO PMO ([contact]) are notified within 5 business days with a full justification and description of the event.

14.8 Case Report Forms

The Principal Investigator and/or his/her designee, will prepare and maintain adequate and accurate participant case histories with observations and data pertinent to the study. Study specific Case Report Forms (CRFs) will document protocol-required outcomes for safety monitoring and data analysis. All study data will be entered electronically in an Electronic Data Capture system in accordance with the protocol schedule of events and guidelines developed in the Data Management Plan for the study, using a secure access account.

All protocol data is the sole property of UFHCC and should not be made available in any form to third parties, except for authorized representatives of appropriate Health/Regulatory Authorities, without written permission from UFHCC.

14.9 Record Retention

Study documentation includes all eCRFs, data correction forms or queries, source documents, Sponsor-Investigator correspondence, monitoring logs/letters, and regulatory documents (e.g., protocol and amendments, IRB correspondence and approval, signed subject consent forms).

Source documents include all recordings of observations or notations of clinical activities and all reports and records necessary for the evaluation and reconstruction of the clinical research study.

Government agency regulations and directives require that all study documentation pertaining to the conduct of a clinical trial must be retained by the study investigator. In the case of a study with a drug seeking regulatory approval and marketing, these documents shall be retained for at least two years after the last approval of marketing application in an International Conference on Harmonization (ICH) region. In all other cases, study documents should be kept on file until three years after the completion and final study report of this investigational study.

UF Health Cancer Center requires that all study documentation be maintained for at least 6 years from the date of final study publication. No study records may be destroyed without

prior authorization from UF.

16. APPENDICES

(Page intentionally left blank. Please proceed to the following page.)

Appendix A: Infection Definitions

Type of Infection	Clinical/Radiographic Criteria	Laboratory/Microbiological
Major Infections		
Primary Blood BSI²⁰	Organism(s) identified in blood is not related to an infection at another site	
 Pathogen cultured from ≥ 1 blood cultures Cultured organism(s) are other than common skin contaminants
Primary BSI with Skin Colonizers²⁰	
 Patient has at least one of the following signs or symptoms: fever ($> 38.0^{\circ}\text{C}$), chills, or hypotension AND Organism(s) identified from blood is not related to an infection at another site AND The same common commensal (i.e., diphtheroids [Corynebacterium spp. not C. diphtheriae], Bacillus spp. [not B. anthracis], Propionibacterium spp., coagulase-negative staphylococci [including S. epidermidis], viridans group streptococci, Aerococcus spp., and Micrococcus spp.]) is identified 	
 ≥ 2 blood specimens drawn on separate occasions (collected on the same or consecutive calendar days) Collected in a manner which suggests that 2 separate blood draw site preparations were performed (e.g., different venipunctures, a combination of venipuncture and lumen withdrawal, or different lumens of the same central line)
Pneumonia²¹	All of the following criteria are met: 
 Chest imaging (either chest X-ray or computed tomography scan) consistent with pneumonia; AND 	
 The presence of the clinical pneumonia syndrome in conjunction with the isolation of a probable pulmonary pathogen from the blood, sputum, BAL fluid, or lung tissue.

Type of Infection	Clinical/Radiographic Criteria	Laboratory/Microbiological
	
 • No evidence of pulmonary edema based on echocardiographic and pulmonary artery catheter data, fluid balance, and radiographic response to diuresis; AND • Temperature greater than 38°C*, OR dyspnea, OR cough with purulent sputum 
*Fever may be absent in a minority of patients and some may even be hypothermic.
	
 • Coagulase-negative Staphylococcus and Candida species will be excluded unless there is biopsy-proven invasion or concomitant isolation of the organism in respiratory secretions and blood in the absence of a more likely pulmonary pathogen. • A virus will be considered a pathogen if it is detected by antibody or culture or polymerase chain reaction from respiratory secretions in the absence of a more likely etiologic agent
CMV Pneumonia (Proven)²⁰	
 • Clinical symptoms and/or signs of pneumonia such as new infiltrates on imaging, hypoxia, tachypnea, and/or dyspnea AND • CMV documentation in lung tissue 	CMV documented in lung tissue by virus isolation, rapid culture, histopathology, immunohistochemistry, or DNA hybridization techniques
CMV Pneumonia (Probable)²²	
 • Clinical symptoms and/or signs of pneumonia AND • Detection of CMV 	CMV by viral isolation, rapid culture of BAL fluid, or the quantitation of CMV DNA in BAL fluid. A definite cut-off for CMV DNA load is not established
Proven Lower RVI²³	New pulmonary infiltrates per CT chest or chest X-ray with or without lower respiratory tract symptoms	Respiratory virus detected with BAL or biopsy specimen by multiplex-PCR
Probable Lower RVI²³	No new pulmonary infiltrates per CT chest or chest X-ray with lower respiratory tract symptoms, with or without pulmonary function decline	Respiratory virus detected in BAL or lung biopsy sample by multiplex-PCR

Type of Infection	Clinical/Radiographic Criteria	Laboratory/Microbiological
Proven IFI²⁴ Only laboratory/microbiological criteria	
Microscopic analysis
 
Mold: Histopathologic, cytopathologic, or direct microscopic examination of a specimen obtained by needle aspiration or biopsy in which hyphae or melanized yeast-like forms are seen accompanied by evidence of associated tissue damage
 
Yeast: Histopathologic, cytopathologic, or direct microscopic examination of a specimen obtained by needle aspiration or biopsy from a normally sterile site (other than mucous membranes) showing yeast cells—for example, Cryptococcus spp. indicated by encapsulated budding yeasts or Candida spp. showing pseudohyphae or true hyphae
 
Culture (sterile material)
 
Mold: Recovery of a mold or “black yeast” by culture of a specimen obtained by a sterile procedure from a normally sterile and clinically or radiologically abnormal site consistent with an infectious disease process, excluding BAL fluid, a cranial sinus cavity specimen, and urine
	
 • Blood culture that yields a mold (e.g., Fusarium species) in the context of a compatible infectious disease process • Blood culture that yields yeast (e.g., Cryptococcus or Candida spp.) or yeast like fungi (e.g., Trichosporon species) • Cryptococcal antigen in CSF indicates disseminated cryptococcosis

Type of Infection	Clinical/Radiographic Criteria	Laboratory/Microbiological
	Yeast: Recovery of a yeast by culture of a sample obtained by a sterile procedure (including a freshly placed [<24 h ago] drain) from a normally sterile site showing a clinical or radiological abnormality consistent with an infectious disease process	
Probable IFI²⁴ Subjects MUST have one each (at a minimum) of host, clinical, and microbiologic criteria	
Host criteria:
 
 Recent history of neutropenia (< 500 cells/mm³ for > 10 days) temporally related to onset of fungal disease; OR Received an allogeneic HSCT; OR Corticosteroid use for > 3 weeks (average dose 0.3 mg/kg/d prednisone equivalent); OR Treatment with T-cell immune suppressants (e.g., cyclosporine, TNFα blocker, specific monoclonal antibodies or nucleoside analogues) within the last 90 days; OR Inherited severe immunodeficiency; 
Clinical criteria:
 
 Lower respiratory tract fungal disease (1 of 3 on CT scan): 
 Dense, well circumscribed lesion(s) with or without a halo sign; OR 	
Microbiologic criteria
 
 Mold in sputum, BAL fluid, bronchial brush, or sinus aspirate samples, indicated by 1 of either presence of fungal elements indicating a mold or recovery of a mold by culture (e.g., Aspergillus, Fusarium, Zygomycetes, or Scedosporium spp.); OR Positive evidence of GM in serum, BAL or CSF; OR Positive evidence of β-D-glucan in serum

Type of Infection	Clinical/Radiographic Criteria	Laboratory/Microbiological
	
 ○ Air-crescent sign; OR ○ Cavity; OR • Tracheobronchitis (mark the finding(s) per bronchoscopic evaluation) 
 ○ Tracheobronchial ulceration; OR ○ Nodule; OR ○ Pseudo-membrane; OR ○ Plaque or eschar; OR • Sinonasal Infection (imaging showing sinusitis plus 1 of the following 3 signs): 
 ○ Acute localized pain (including pain radiating to the eye); OR ○ Nasal ulcer with black eschar; OR ○ Extension of the paranasal sinus process across bony barriers; OR • CNS Infection (1 of the following): 
 ○ Focal lesions on imaging; OR ○ Meningeal enhancement on MRI or CT; 	

Type of Infection	Clinical/Radiographic Criteria	Laboratory/Microbiological
	
OR
 
 • Disseminated candidiasis (at least 1 of the followings after an episode of candidemia within the previous 2 weeks): 
 ◦ Small target-like abscesses (bull's eye lesions) in liver or spleen; OR ◦ Progressive retinal exudates on ophthalmologic examination 	
Clostridium difficile infection (CDI)²⁵ Diagnosis will be if the clinical criterion is met AND there is microbiological confirmation	Presence of at least 3 unformed bowel movements in a 24-hour period or fewer consecutive hours	
 • A stool test result positive for the presence of toxigenic C. difficile or its toxins or colonoscopic OR histopathologic findings demonstrating pseudomembranous colitis • Patients presenting with ileus or megacolon will need a perianal specimen test positive for C. difficile or its toxins
Typhilitis²⁶ Diagnosis will be if the clinical criteria are met AND there is microbiological confirmation	
 • Patients with fever > 38.3°C * or > 38°C sustained for 1 hour, neutropenia and abdominal signs such as abdominal cramping, abdominal pain (> 3 on VAS), abdominal distention, diarrhea, GI bleeding AND • Exclusion of other diagnoses such as C. difficile associated colitis or other biopsy proven diagnosis 	
 • ANC ≤ 500/mm³ AND • Bowel wall thickening on CT exam or US exam > 4 mm (transverse scan) thickening in any segment of the bowel for at least 30 mm length (longitudinal scan)

Type of Infection	Clinical/Radiographic Criteria	Laboratory/Microbiological
	*Fever may be absent in a minority of patients and some may even be hypothermic.	
Other Infections		
Febrile Neutropenia²⁷ Both clinical and laboratory criteria should be met	
 • A single oral temperature of $> 38.3^{\circ}\text{C}$ (101°F) OR • A temperature of $> 38.0^{\circ}\text{C}$ (100.4°F) sustained for > 1 hour 	
 • ANC < 500 cells/mm^3 OR • ANC that is expected to decrease to < 500 cells/mm^3 during the next 48 hours
Upper RVI²³	
 • No new pulmonary infiltrates per CT chest or chest X-ray • Symptoms of upper respiratory tract infection 	Respiratory virus detected in a nasopharyngeal swab or sputum by multiplex-PCR
Possible Lower RVI²³	New pulmonary infiltrates per CT chest or chest X-ray (but without confirmation of respiratory virus in the lower respiratory tract) with or without LRTD signs or symptoms (e.g., cough, wheezing, rales, tachypnea, shortness of breath, dyspnea, or hypoxia).	Respiratory virus detected in a nasopharyngeal swab or sputum by multiplex-PCR
Catheter-associated BSI for Non-skin common skin contaminants²⁰ BOTH clinical and microbiological criteria should be met	
 • A CVC must be present at the time of the BSI or removed within the 48 hours prior to onset, unless clinical evidence links the BSI to a catheter removed > 48 hours before onset (e.g., purulent thrombophlebitis) AND • Absence of other focus of infection as a source of the BSI 	Recognized pathogen cultured (other than skin contaminants) from one or more blood cultures, unrelated to infection at another site
Septic Shock²⁸	
 • Any documented infection AND 	Lactate > 2 mmol/L (> 18 mg/dL)

Type of Infection	Clinical/Radiographic Criteria	Laboratory/Microbiological
	
 Requirement of vasopressors and have a lactate >2 mmol/L (>18 mg/dL) 	
Catheter associated BSI for common skin contaminants²⁰ (e.g. diphtheroids, Bacillus spp, Propionibacterium spp, coagulase negative staphylococci, and micrococci) BOTH clinical and microbiological criteria should be met	
At least one of the following:
 
 Fever (> 38°C) Chills Hypotension Signs of infection of catheter insertion site or tunnel 	
 Organisms (diphtheroids, Bacillus spp., Propionibacterium spp., coagulase negative staphylococci, and micrococci) cultured from: 
 At least two separate blood draws collected on the same or consecutive calendar days, OR Collected in a manner which suggests that 2 separate blood draw site preparations were performed (e.g., different venipunctures, a combination of venipuncture and lumen withdrawal, or different lumens of the same central line)

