2.2.2 Secondary endpoint(s)

- To determine the safety of HiDAC 123 compared to standard HiDAC 135 in case controls by evaluating the differences in:
 - duration of neutropenia and thrombocytopenia (see neutropenia definition above). Thrombocytopenia is defined as the interval between the first day of platelets < 50x10³/uL after consolidation chemotherapy to the first day of recovery (defined as first day of platelets > 20x10³/uL if consecutive x 2 and not transfused)
 - incidence of documented infections (bloodstream infection (BSI), pneumonia, invasive fungal infection (IFI), Clostridium difficile infection (CDI), typhlitis, (see Appendix A) and rates of febrile neutropenia (defined as temperature \geq 38.3 C° once or \geq 38 C° for more than 1 hour and ANC less than 500/mm³ or expected to fall below 500/mm³ in next 48 hours)
 - number of RBC and platelet transfusions given per cycle will be recorded in units
 - readmission rates (incidence and reason for admission) and LOS recorded in days (total, including chemotherapy administration, and readmission days)
 - non-hematologic toxicity: focus on CNS/cerebellar and ocular as these are specific to high dose cytarabine, but will record incidences of any other grade 3-5 organ systems according to CTCAE v5 criteria
 - time to next treatment (next chemotherapy cycle, transplant, etc.; if chemotherapy was discontinued prior to planned date, what was the reason)

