7.3.3 Infections

Chemotherapy puts the patient at higher risk for bacterial, viral, or fungal infections, which are potentially life-threatening. Prophylactic antimicrobial medications and prophylactic granulocyte colony stimulating factor will be initiated per institutional guidelines if able, and patients will be closely monitored for signs of infections and will receive early and appropriate treatment per standard of care. Infections will be scored according to infections listed in Appendix A.

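### Appendix A's C. difficile row excludes ileus or megacolon cases that its own specimen rule is written to capture

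*Combined protocol and SAP*

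**What the plan says.** Section 2.2.2 makes infection a secondary safety endpoint: "incidence of documented infections (bloodstream infection (BSI), pneumonia, invasive fungal infection (IFI), Clostridium difficile infection (CDI), typhlitis", with a pointer to Appendix A. Section 7.3.3 makes the appendix the scoring rule: "Infections will be scored according to infections listed in Appendix A".

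The CDI row of Appendix A has three parts:

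- Combination rule, under the row name: "Diagnosis will be if the clinical criterion is met AND there is microbiological confirmation".
- Clinical column, single entry: "Presence of at least 3 unformed bowel movements in a 24-hour period or fewer consecutive hours".
- Laboratory/microbiological column: a positive stool test, or colonoscopic or histopathologic evidence of pseudomembranous colitis. A second bullet follows: "Patients presenting with ileus or megacolon will need a perianal specimen test positive for" the organism or its toxins.

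The typhlitis row is built the same way: "Diagnosis will be if the clinical criteria are met AND there is microbiological confirmation". Its right-hand column lists an ANC limit together with imaging: "Bowel wall thickening on CT exam or US exam > 4 mm (transverse scan) thickening in any segment of the bowel". It names no culture, organism or toxin test.

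Section 12.4 summarizes secondary endpoints descriptively, with exploratory group comparisons. Section 12.3 lists documented infection in the first consolidation (yes or no) among the covariates of the adjusted model for neutropenia duration.

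**The concern.** The second laboratory bullet in the CDI row has a purpose only if patients with ileus or megacolon can be scored as CDI on a perianal specimen. The combination rule still holds them to the stool count. If a patient has ileus or megacolon and does not reach three unformed stools, the specimen result makes no difference. Whoever scores the chart must either drop a case that the row evidently means to include or depart from the written rule.

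What is at stake is the CDI tally within one secondary safety endpoint. The yes/no infection covariate in the adjusted model of section 12.3 could also be affected, if the missed case is that patient's only documented infection in cycle 1.

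**Working it through.** The plan states no figure on this point, so there is none to reproduce. The check is of the logic of the row.

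**Inputs, all from the CDI row of Appendix A.** Four yes/no facts per patient:

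- S: stool count met.
- I: ileus or megacolon.
- T: positive stool test, or colonoscopic or histopathologic finding.
- P: positive perianal specimen.

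**Rules compared.**

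- Row followed exactly: CDI = S and C, where C (confirmation) is P if I is yes, and T otherwise.
- Ileus or megacolon as its own route: CDI = P if I is yes, and (S and T) otherwise.

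**Result over the 2 × 2 × 2 × 2 = 16 combinations.**

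| Ileus or megacolon | Stool count met | Perianal specimen | Combinations | Row followed exactly | Own route |
|---|---|---|---|---|---|
| No | either | either | 8 | CDI if S and T | same |
| Yes | yes | positive | 2 | CDI | CDI |
| Yes | yes | negative | 2 | not CDI | not CDI |
| Yes | no | positive | 2 | **not CDI** | **CDI** |
| Yes | no | negative | 2 | not CDI | not CDI |

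The rules agree in 14 combinations and differ in 2. Both are ileus or megacolon with a positive perianal specimen and too few unformed stools, and they differ only in T. These are counts of logical cases, not frequencies.

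The exclusion does not depend on how the two laboratory bullets combine. The stool count is joined to confirmation by AND, so with S = no the row fails whatever the tests show. Ordinary diarrheal CDI with a positive test is counted under both rules.

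**Size.** The documents give no rate of CDI, ileus or megacolon. Assuming zero or one affected subject per cohort of 29, the CDI incidence in that cohort shifts by 0/29 = 0 to 1/29 = 3.4 percentage points.

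**Typhlitis row.** If the confirmation phrase refers to the column headed Laboratory/Microbiological, a febrile patient with abdominal signs, other diagnoses excluded, low ANC and bowel wall thickening is scored. If it required an organism, the same patient would fail without one, and the table names no qualifying test. The first reading gives every entry in the row a function; the second leaves the listed ANC and imaging criteria insufficient with nothing named to complete them. The first is the natural reading. An afebrile case depends on whether the row's footnote, which says that fever may be absent, is taken as a waiver.

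**The case against.** The case for leaving the row alone has four parts:

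- A scorer may read the ileus and megacolon bullet as its own route, since a specific provision usually overrides a general one. This is plausible, but it requires ignoring an explicit AND with no stated exception, and the bullet sits in the confirmation column.
- The stool count has no timing link to the ileus, so a patient with three unformed stools beforehand still qualifies. This is correct and narrows the affected group. The documents do not say how often patients with ileus or megacolon miss the count.
- In the prospective arm, sections 11.2 and 11.3 require grade 3-5 toxicities and associated infections to be recorded, and SAEs are collected from consent. A severe case is therefore not lost to safety reporting. This stands, but the case still drops out of the infection endpoint compared with controls.
- The endpoint is descriptive, and the stopping boundary in section 12.7 uses neurological toxicity only. This also stands, and it is why the point is minor.

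A reader might go further and infer that the typhlitis rule cannot be met either, so that two of the five named infections are undercounted. With an assumed typhlitis incidence of 5-10%, that would lose 29 × 0.05 = 1.5 to 29 × 0.10 = 2.9 subjects per cohort. The documents do not support this. The incidence is not theirs, and on the natural reading febrile, imaging-confirmed typhlitis is scored. In favor of the stricter reading, the febrile neutropenia row speaks of laboratory criteria where its column holds only ANC, and the catheter-associated BSI rows say microbiological where they list cultures. That shows loose wording in the typhlitis row, not an impossible rule.

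**Conclusion.** The CDI row is wrong as written, in a minor way. It rejects patients with ileus or megacolon, a positive perianal specimen and fewer than three unformed stools, although its own bullet provides for such patients. The number affected is probably zero or one per cohort. That is an assumption, because the documents contain no rate from which to estimate it. The primary t-test and the sample size are untouched. Any effect on the adjusted model of section 12.3 is only possible and would run through a single covariate.

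A reader might also infer that the cohorts would be scored differently because controls were treated between 2/1/2017 and 2/1/2019. Section 3.1 gives those as treatment dates, and no section says when the control charts are abstracted. The same definitions apply to both cohorts. Inconsistent scoring of a contradictory rule is conceivable, but no between-cohort bias is shown.

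**What to change.** In the CDI row, rewrite the clinical criterion for endpoint scoring as: *three or more unformed stools within 24 hours, OR ileus or megacolon with a positive perianal specimen*. Keep the existing confirmation requirement for patients who enter by the stool count, and keep the perianal specimen as the confirmation for patients with ileus or megacolon. With that pairing, the edit changes the result in exactly the two combinations identified above and in no others. Apply it identically to prospective subjects and historical controls.

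As a wording clean-up only, replace the reference to microbiological confirmation in the typhlitis row with *the laboratory and imaging criteria in the right-hand column are met*.

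The cost is two wording changes in Appendix A, with no new data or procedures. They can go into the next amendment, which needs IRB approval under section 14.7. Both concern how an endpoint is counted, not how patients are diagnosed or treated.
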